4.13	Distance Over-Refraction and Distance Visual Acuity	Perform a distance over-refraction OD and OS using loose lenses outside of the phoropter under ambient room illumination. The distance over-refraction may also be refined under binocular conditions. Record the results. The results of the distance over-refraction may also be checked for the impact on near vision under monocular and/or binocular conditions.	
4.14	Lens Fit Assessment	
Evaluate overall lens fit acceptance (acceptable or unacceptable) based on centration, movement and other fitting characteristics.
 
An unacceptable fit is deemed by one of the following criteria:
 
 • limbal exposure at primary gaze or with extreme eye movement; • edge lift; • excessive movement in primary and up gaze; or 	

Clinical Study Protocol
Johnson & Johnson Vision Care, Inc.

		
 insufficient movement in all three of the following conditions: primary gaze, up gaze, and Josephson push up. 
If either lens is deemed unacceptable, the subject will be discontinued from the study. Remove the lenses, perform a slit-lamp evaluation, and complete the Final Evaluation form.
	
4.15	Modifications	
If the subject reports unsatisfactory vision, or is unable to obtain 20/30 distance visual acuity OU with the lenses then a modification must be attempted.
 
If the subject reports satisfactory vision with the lenses a modification is not required, however at the Investigator's discretion and based upon their findings on the measured visual acuity and/or over- refraction the investigator may make a modification.
 
Up to two attempts at modification are permitted if necessary, in order to achieve an acceptable distance and near binocular performance for the subject, and to enable them to wear that particular lens type. Follow the fitting guide allowing for at least 10 minutes of settling time between each lens modification attempted.
 
If modifications are required steps 4.8-4.14 will be repeated for each modification
	Appendix G (Fitting Guide)
4.16	Post-Fit PRO (MRD) Questionnaire	The subject will evaluate the vision characteristics, comfort characteristics, handling characteristics, and visual symptoms of the study lenses using the PRO questionnaire.	
4.17	Distance and Near Exit Visual Acuity	
Distance and near Snellen visual acuity will be measured for each eye with the study contact lenses in place.
 
For near measures use the ETDRS 2000 Series Chart 1 or 2.
 
The acuity will be recorded to the nearest letter OD, OS and OU.
 
Note: The distance visual acuity must be at least 20/30 OU for the lenses to be dispensed.
	
4.18	Dispensing Criteria	The lenses will be dispensed for 2-4 days.	

Clinical Study Protocol
Johnson & Johnson Vision Care, Inc.

		
 • Distance Snellen acuity equal to or better than 20/30 OU • Subject must indicate that the vision is acceptable. • Subject must indicate that the comfort of the lenses is acceptable. • Lenses must have an acceptable general lens fit. 	
4.19	Patient Instructions for Daily Disposable Lenses (if applicable)	
Instruct the Subject the following:
 
 • The lenses will be worn on a daily wear basis. • Only enough lenses will be dispensed to the subject to wear for the required number of days until their follow-up visit. No additional lenses will be dispensed. • A new lens will be opened and worn each day. • Instruct the subject to bring back all unworn study lenses. • No cleaning or disinfecting solutions will be used. If determined necessary by the Investigator sterile non-preserved rewetting drops may be dispensed to be used as needed for dryness. • Subjects will be instructed to wear lenses for a minimum of 6 hours a day, every day during the study. • Subjects will be instructed to wear their glasses when not wearing the study lenses. 
Note: In the event a lens is lost or damaged, the subject will return to the investigator site for replacement. As much as reasonably possible, a damaged lens should be returned to the investigational site and then returned to the Sponsor. If lens damage is present, complete the Product Quality Complaint Form. The lens will be stored in labeled vial with sterile saline, and returned to the Sponsor.
	

Clinical Study Protocol
Johnson & Johnson Vision Care, Inc.

4.20	Patient Instructions for Daily Reusable Wear Lenses (if applicable)	
Instruct the Subject the following:
 
 • The lenses will be worn on a daily wear basis. • OPTI-FREE® Replenish® solution will be used in a rub regime to disinfect and store the lenses each night in the lens case provided. • If determined necessary by the Investigator sterile non-preserved rewetting drops may be dispensed to be used as needed for dryness. • Subjects will be instructed to wear lenses for a minimum of 6 hours a day, every day during the study. • Subjects will be instructed to wear their glasses when not wearing the study lenses. • A patient instruction booklet will be provided. 
Note: In the event a lens is lost or damaged, the subject will return to the investigator site for replacement. As much as reasonably possible, a damaged lens should be returned to the investigational site and then returned to the Sponsor. If lens damage is present, complete the Product Quality Complaint Form. The lens will be stored in labeled vial with sterile saline, and returned to the Sponsor.
	
4.21	Schedule Follow-up	
The subject will be scheduled to return for their follow-up appointment in 3±1 days.
 
Note: To count the follow-up visit as a day of wear the Subject must have worn the study lenses for 6 hours prior to the visit.
	

VISIT 5

The subjects must present to Visit 5 wearing the study lenses. To be counted as a day of wear the lenses need to have been worn for at least six (6) hours prior to the visit.

Visit 5: Treatment 2 Follow-up 1		
Step	Procedure	Details
		[REDACTED]

Clinical Study Protocol
Johnson & Johnson Vision Care, Inc.

5.1	Adverse Events and Concomitant Medications Review	Review the subject's concomitant medications and record any changes from the previous study visit. Record any adverse events or medical history changes from the previous study visit.	
5.2	Wear time and Comfortable Wear time with Study lenses	Record the hours the subject has worn the study lenses and the comfortable wear time on the day of follow-up.	
5.3	Compliance	Record the subject's compliance with wearing the study lenses. Note: Subjects must have worn lenses for at least 6 hours per day To be counted as a day of wear at this visit the Subject must have worn the study lenses for 6 hours prior to the visit.	
5.4	PRO (CLUE) Questionnaire	The subject will evaluate the vision characteristics, comfort characteristics, handling characteristics, and visual symptoms of the study lenses using the PRO questionnaire.	
5.5	Ocular Symptoms	Subjects will respond to a verbal open-ended symptoms questionnaire	
5.6	Subjective Acceptance	Record whether the subject's distance and near vision with the lenses is acceptable.	
5.7	Distance and Near Entrance Visual Acuity	Distance and near Snellen visual acuity will be measured for each eye with the study contact lenses in place. For near measures use the ETDRS 2000 Series Chart 1 or 2. The acuity will be recorded to the nearest letter OD, OS and OU.	
5.8	Distance Over-Refraction and Distance Visual Acuity	Perform a distance over-refraction OD and OS using loose lenses outside of the phoropter under ambient room illumination. The distance over-refraction may also be refined under binocular conditions. Record the results and distance visual acuity OD and OS. The results of the distance over-refraction may also be checked for the impact on near vision under monocular and/or binocular conditions.	

Clinical Study Protocol
Johnson & Johnson Vision Care, Inc.

5.9	Determination of Lens Optimization	
If the subject reports unsatisfactory vision, or is unable to obtain 20/30 distance visual acuity OU with the lenses then a modification must be attempted.
 
If the subject reports satisfactory vision with the lenses a modification is not required, however at the Investigator's discretion and based upon their findings on the measured visual acuity and/or over- refraction the investigator may make a modification.
 
Up to two attempts at modification are permitted if necessary, in order to achieve an acceptable distance and near binocular performance for the subject, and to enable them to wear that particular lens type.
 
Follow the fitting guide and steps 4.8-4.14 in Visit 4 Fitting, allowing for at least 10 minutes of settling time between each lens modification.
	Appendix G (Fitting Guide)
5.10	Lens Fit Assessment	
Evaluate and grade lens centration, primary gaze movement, upgaze movement and tightness (push-up test).
 
The subject should not proceed to wear the lenses if any of the following is observed:
 
 • presence of limbal exposure (appearance of clear cornea) in any gaze • presence of edge lift • presence of unacceptable movement (excessive or insufficient) in all three movement categories (primary gaze, upgaze, and push-up). 
If either lens is deemed unacceptable, the subject will be discontinued from the study. Remove the lenses, perform a slit-lamp evaluation, and complete the Final Evaluation form.
	[REDACTED]
5.11	Collection of unworn lenses (if applicable)	
Collect unworn lenses returned by the subject when lens power has been optimized
 
Note: If lens power was not changed allow the subject to use the unworn lenses dispensed at Visit 4 and dispense enough
	[REDACTED]

Clinical Study Protocol
Johnson & Johnson Vision Care, Inc.

		
lenses of the same power to last the subject until their next visit.
	
5.12	Lens Removal	
The study lenses will be removed and discarded.
	
5.13	Biomicroscopy	
Perform biomicroscopy OD and OS. Slit Lamp Classification Scales will be used to grade the findings.
 
For the conjunctival redness [REDACTED] 0.5 unit increments will be used in the grading.
 
Corneal Staining Assessment [REDACTED] will be graded in 1.0 increments.
 
If any of these slit lamp findings are Grade 3 or higher, an AE must be recorded. All AEs must be followed to resolution.
 
If the clearance of the fluorescein needs to be expedited, preservative-free rewetting drops may be instilled.
	[REDACTED]
5.14	Insertion of Study Lenses	
Dispense the subject new lenses that match the distance and ADD power of the lenses that were removed in Step 5.12 above.
	
5.15	PRO (MRD) Questionnaire	
The subject will evaluate the vision characteristics, comfort characteristics, handling characteristics, and visual symptoms of the study lenses using the PRO questionnaire.
	
5.16	Distance and Near Exit Visual Acuity	
Distance and near Snellen visual acuity will be measured for each eye with the study contact lenses in place.
 
For near measures use the ETDRS 2000 Series Chart 1 or 2.
 
The acuity will be recorded to the nearest letter OD, OS and OU.
 
Note: The distance visual acuity must be at least 20/30 OU for the lenses to be dispensed.
	[REDACTED]
5.17	Dispensing Criteria	
The lenses will be dispensed for 10-14 days.
 
 • Distance Snellen acuity equal to or better than 20/30 OU • Subject must indicate that the vision is acceptable. • Subject must indicate that the comfort of the lenses is acceptable. 	

Clinical Study Protocol
Johnson & Johnson Vision Care, Inc.

		
 • Lenses must have an acceptable general lens fit. 	
5.18	Patient Instructions for Daily Disposable Lenses	
Instruct the Subject the following:
 
 • The lenses will be worn on a daily wear basis. • Only enough lenses will be dispensed to the subject to wear for the required number of days until their follow-up visit. No additional lenses will be dispensed. • A new lens will be opened and worn each day. • Instruct the subject to bring back all unworn study lenses. • No cleaning or disinfecting solutions will be used. If determined necessary by the Investigator sterile non-preserved rewetting drops may be dispensed to be used as needed for dryness. • Subjects will be instructed to wear lenses for a minimum of 6 hours a day, every day during the study. • Subjects will be instructed to wear their glasses when not wearing the study lenses. • Subjects will be instructed to bring their habitual contacts or spectacles to the next visit. 
Note: In the event a lens is lost or damaged, the subject will return to the investigator site for replacement. As much as reasonably possible, a damaged lens should be returned to the investigational site and then returned to the Sponsor. If lens damage is present, complete the Product Quality Complaint Form. The lens will be stored in labeled vial with sterile saline, and returned to the Sponsor.
	
5.19	Patient Instructions for Daily Reusable Wear Lenses	
Instruct the Subject the following:
 
 • The lenses will be worn on a daily wear basis. 	

Clinical Study Protocol
Johnson & Johnson Vision Care, Inc.

		
 • OPTI-FREE® Replenish® solution will be used in a rub regime to disinfect and store the lenses each night in the lens case provided. • If determined necessary by the Investigator sterile non-preserved rewetting drops may be dispensed to be used as needed for dryness. • Subjects will be instructed to wear lenses for a minimum of 6 hours a day, every day during the study. • Subjects will be instructed to wear their glasses when not wearing the study lenses. • Subjects will be instructed to bring their habitual contacts or spectacles to the next visit. 
Note: In the event a lens is lost or damaged, the subject will return to the investigator site for replacement. As much as reasonably possible, a damaged lens should be returned to the investigational site and then returned to the Sponsor. If lens damage is present, complete the Product Quality Complaint Form. The lens will be stored in labeled vial with sterile saline, and returned to the Sponsor.
	
5.20	Schedule Follow-up	
The subject will be scheduled to return for their follow-up appointment in 12±2 days.
 
Note: To count the follow-up visit as a day of wear the Subject must have worn the study lenses for 6 hours prior to the visit.
	

Clinical Study Protocol
Johnson & Johnson Vision Care, Inc.

VISIT 6

The subjects must present to Visit 6 wearing the study lenses. To be counted as a day of wear the lenses need to have been worn for at least six (6) hours prior to the visit.

Visit 6: Treatment 2 Follow-up 2		
Step	Procedure	Details
6.1	Adverse Events and Concomitant Medications Review	
Review the subject's concomitant medications and record any changes from the previous study visit.
 
Record any adverse events or medical history changes from the previous study visit.

6.2	Wear time and Comfortable Wear time with Study lenses	Record the hours the subject has worn the study lenses and the comfortable wear time on the day of follow-up.
6.3	Compliance	
Record the subject's compliance with wearing the study lenses.
 
Note: Subjects must have worn lenses for at least 6 hours per day To be counted as a day of wear at this visit the Subject must have worn the study lenses for 6 hours prior to the visit.

6.4	PRO (CLUE and MRD) Questionnaires and CLDEQ-8	The subject will evaluate the vision characteristics, comfort characteristics, handling characteristics, and visual symptoms of the study lenses using the PRO questionnaire.
6.5	Ocular Symptoms	Subjects will respond to a verbal open-ended symptoms questionnaire
6.6	Subjective Acceptance	Record whether the subject's distance and near vision with the lenses is acceptable.
6.7	Distance and Near Entrance Visual Acuity	
Distance and near Snellen visual acuity will be measured for each eye with the study contact lenses in place.
 
For near measures use the ETDRS 2000 Series Chart 1 or 2.
 
The acuity will be recorded to the nearest letter OD, OS and OU.

6.8	Visual Performance Distance (4M) Intermediate (64 cm) Near (40 cm)	
Visual performance will be recorded OD, OS, and OU for the following:
 
Distance, Bright Illuminance High and Low Contrast ETDRS Charts 4M- HC#1, HC#2, HC#3 and LC#1, LC#2,

Clinical Study Protocol
Johnson & Johnson Vision Care, Inc.

		
LC#3
 
Near, Bright Illuminance
 
Reduced Guillon-Poling Charts
 
Intermediate (64 cm) High Contrast and Low Contrast
 
Near (40 cm) High Contrast and Low Contrast
 
Distance, Dim Illuminance (with Distance goggles)
 
High Contrast ETDRS Charts
 
4M-HC#4, HC#5, HC#6
 
Near, Dim Illuminance (with Near goggles)
 
Reduced Guillon-Poling charts
 
High Contrast Intermediate (64 cm) and Near (40 cm).
 
Note:
 
 • The room illuminance must be between 7.3 and 7.9 EV (394-597 lux). • Distance, HC-1 Chart luminance Acceptable Range 10.5-10.7 EV (181-208 cd/m²). • Guillon-Poling, Near Chart Luminance Acceptable Range 10.8-11.1 EV (223-274 cd/m²). • Do not use the Mesopic filter for Dim luminance (Dim luminance will be simulated by using the goggles) 	
6.9	Binocular Distance Over-refraction and Distance Visual Acuity	
Perform a binocular over-refraction and record the OD and OS results and distance visual acuity.
 
Note: No lens changes are allowed based on the over-refraction.
	Appendix D
6.10	Lens Fit Assessment	
Evaluate and grade lens centration, primary gaze movement, upgaze movement and tightness (push-up test).
 
The subject should not proceed to wear the lenses if any of the following is observed:
 
 • presence of limbal exposure (appearance of clear cornea) in any gaze • presence of edge lift • presence of unacceptable movement (excessive or insufficient) in all three 	

Clinical Study Protocol
Johnson & Johnson Vision Care, Inc.

		
movement categories (primary gaze, upgaze, and push-up).
 
If either lens is deemed unacceptable, the subject will be discontinued from the study. Remove the lenses, perform a slit-lamp evaluation, and complete the Final Evaluation form.
	
6.11	Lens Deposits	Grade and record the amount of front and back surface lens deposits for both eyes.	[REDACTED]
6.12	Lens Wettability	Grade the wettability of the lens.	[REDACTED]
6.13	Collection of unworn lenses (if applicable)	Collect unworn lenses returned by the subject.	
6.14	Lens Removal	
Have the subject remove the study lenses and store in saline in a labeled glass vial.
 
Note: The lenses do not need to be stored in a refrigerator.
	
6.15	Biomicroscopy	
Perform Biomicroscopy OD and OS. Slit Lamp Classification Scales will be used to grade the findings.
 
For the conjunctival redness [REDACTED] 0.5 unit increments will be used in the grading.
 
Corneal Staining Assessment [REDACTED] will be graded in 1.0 increments.
 
If any of these slit lamp findings are Grade 3 or higher, an AE must be recorded. All AEs must be followed to resolution.
 
If the clearance of the fluorescein needs to be expedited, preservative-free rewetting drops may be instilled.
	[REDACTED]

FINAL EVALUATION

The final evaluation will ordinarily take place immediately following the last scheduled follow-up visit per the study protocol. It may also take place at any point the subject discontinues the study or is terminated from the study.

Clinical Study Protocol
Johnson & Johnson Vision Care, Inc.

Final Evaluation		
Step	Procedure	Details
F.1	Distance Subjective Sphero-cylindrical Refraction and Distance Exit Visual Acuity	Perform bare-eye subjective spherocylindrical refraction with a phoropter and record the best corrected distance visual acuity to the nearest letter (OD, OS, and OU). [REDACTED]
F.2	Subject Disposition	Indicate if the subject completed the study successfully. If subject discontinued from the study indicate the reason. [REDACTED]

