1.21	Lens Selection	Select the lens pair and power based on the Randomization and fitting guide for each eye. Record the test lens parameters (power and lot number).	Appendix G (Fitting Guide)
1.22	Lens Insertion	
Subjects will insert the lenses themselves. If the lens is uncomfortable, inspect for damage and remove, reinsert or replace as necessary.
 
Damaged lenses will be stored in labeled vial with sterile saline, and clearly differentiated from the other worn lenses that will be shipped back to the Sponsor. Complete the Quality Product Complaint form.
	
1.23	Lens Settling	Allow the study lenses to settle for a minimum of 10 minutes.	
1.24	Determine Visual Satisfaction	Determine if the subject’s vision is acceptable with the lenses. Allow the subject to look down a hallway or out of a window for distance vision assessments, and for them to	

Clinical Study Protocol
Johnson & Johnson Vision Care, Inc.

		read a book, magazine or similar for near vision.	
1.25	Study Lens Distance and Near Visual Acuity	
Measure the distance and near visual acuity OD, OS and OU. Record the results.
 
Note: Use the ETDRS 2000 Series Chart 1 or 2 near card placed at 40 cm to measure the Near visual acuity
	[REDACTED]
1.26	Distance Over-Refraction and Distance Visual Acuity	
Perform a distance over-refraction OD and OS using loose lenses outside of the phoropter under ambient room illumination. The distance over-refraction may also be refined under binocular conditions. Record the results. The results of the distance over-refraction may also be checked for the impact on near vision under monocular and/or binocular conditions.
	
1.27	Lens Fit Assessment	
Evaluate and grade lens centration, primary gaze movement, upgaze movement and tightness (push-up test).
 
 • The subject should not proceed to wear the lenses if any of the following is observed: • presence of limbal exposure (appearance of clear cornea) in any gaze • presence of edge lift • presence of unacceptable movement (excessive or insufficient) in all three movement categories (primary gaze, upgaze, and push-up). 
If either lens is deemed unacceptable, the subject will be discontinued from the study. Remove the lenses, perform a slit-lamp evaluation, and complete the Final Evaluation form.
	[REDACTED]

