2.9	Determination of Lens Optimization	
If the subject reports unsatisfactory vision, or is unable to obtain 20/30 distance visual acuity OU with the lenses then a modification must be attempted.
 
If the subject reports satisfactory vision with the lenses a modification is not required, however at the Investigator's discretion and based upon their findings on the measured visual acuity and/or over-refraction the investigator may make a modification.
 
Up to two attempts at modification are permitted if necessary, in order to achieve an
	Appendix G (Fitting Guide)

Clinical Study Protocol
Johnson & Johnson Vision Care, Inc.

		acceptable distance and near binocular performance for the subject, and to enable them to wear that particular lens type. Follow the fitting guide and steps 1.21-1.27 in Visit 1 Fitting allowing for at least 10 minutes of settling time between each lens modification.	
2.10	Lens Fit Assessment	
Evaluate and grade lens centration, primary gaze movement, upgaze movement and tightness (push-up test).
 
 • The subject should not proceed to wear the lenses if any of the following is observed: • presence of limbal exposure (appearance of clear cornea) in any gaze • presence of edge lift • presence of unacceptable movement (excessive or insufficient) in all three movement categories (primary gaze, upgaze, and push-up). 
If either lens is deemed unacceptable, the subject will be discontinued from the study. Remove the lenses, perform a slit-lamp evaluation, and complete the Final Evaluation form.
	
2.11	Collection of unworn lenses (if applicable)	
Collect unworn lenses returned by the subject when lens power has been optimized
 
Note: If lens power was not changed allow the subject to use the unworn lenses dispensed at Visit 1 and dispense enough lenses of the same power to last the subject until their next visit.
	
2.12	Lens Removal	The study lenses will be removed and discarded.	
2.13	Biomicroscopy	
Perform Biomicroscopy OD and OS. Slit Lamp Classification Scales will be used to grade the findings.
 
For the conjunctival redness [REDACTED] 0.5 unit increments will be used in the grading.
 
Corneal Staining Assessment [REDACTED] will be graded in 1.0 increments.
	

Clinical Study Protocol
Johnson & Johnson Vision Care, Inc.

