The trial lens should be placed on each of the patient's eyes and evaluated after the patient has adjusted to the lenses.

1. Criteria of a Properly Fit Lens

A properly fit lens will center and completely cover the cornea (i.e., no limbal exposure), have sufficient movement to provide tear exchange under the contact lens with the blink, and be comfortable. The lens should move freely when manipulated digitally with the lower lid, and then return to its properly centered position when released.

2. Criteria of a Flat Fitting Lens

A flat fitting lens may exhibit one or more of the following characteristics: decentration, incomplete corneal coverage (i.e., limbal exposure), excessive movement with the blink and/or edge standoff. If the lens is judged to be flat fitting, it should not be dispensed to the patient.

3. Criteria of a Steep Fitting Lens

A steep fitting lens may exhibit one or more of the following characteristics: insufficient movement with the blink, conjunctival indentation, and resistance when pushing the lens up digitally with the lower lid. If the lens is judged to be steep fitting, it should not be dispensed to the patient.

If the initial trial base curve is judged to be flat or steep fitting, the alternate base curve, if available, should be trial fit and evaluated after the patient has adjusted to the lens. The lens should move freely when manipulated digitally with the lower lid, and then return to a properly centered position when released. If resistance is encountered when pushing the lens up, the lens is fitting tightly and should not be dispensed to the patient.

E. Final Lens Power (Spherical)

A spherical over-refraction should be performed to determine the final lens power after the lens fit is judged acceptable. The spherical over-refraction should be combined with the trial lens power to determine the final lens prescription. The patient should experience good visual acuity with the correct lens power unless there is excessive residual astigmatism.

Example 1	
Diagnostic lens:	-2.00D
Spherical over-refraction:	-0.25D
Final lens power:	-2.25D

Example 2	
Diagnostic lens:	-2.00D
Spherical over-refraction:	+0.25D
Final lens power:	-1.75D

If vision is acceptable, perform a slit lamp examination to assess adequate fit (centration and movement). If the fit is acceptable, dispense the lenses and instruct the patient to return in one week for reassessment (see **PATIENT MANAGEMENT** section).

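### The listed lens-fit stop rule is stricter on excessive movement at the period 2 fitting (step 4.14) than at the period 1 fitting (step 1.27)

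*Combined protocol and SAP*

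**What the plan says.** The protocol has seven lens-fit steps: 1.27, 2.10, 3.10, 4.14, 5.10 and 6.10 at the scheduled visits (section 7.2) and U.8 at unscheduled visits (section 7.3). Steps 1.27 and 4.14 are the initial fittings of period 1 and period 2.

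Six of the seven share one text. They open with "Evaluate and grade lens centration, primary gaze movement, upgaze movement and tightness (push-up test", and bar wear for limbal exposure, edge lift, or "presence of unacceptable movement (excessive or insufficient) in all three" movement categories.

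Step 4.14 is worded differently. It opens with "Evaluate overall lens fit acceptance (acceptable or unacceptable) based on centration, movement and other fitting characteristics". Its limbal exposure and edge lift criteria are in substance the same, but it splits movement into two bullets. One is "excessive movement in primary and up gaze", with no push-up condition. The other is insufficient movement in primary gaze, up gaze and push-up together.

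All seven steps end alike: if either lens is judged unacceptable, the subject is discontinued.

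**The concern.** In a 2×2 crossover the two fittings should apply the same stopping rule. Here a subject whose lens moves too much in primary gaze and upgaze, but passes the push-up test, may go on under the period 1 list and is to be discontinued under the period 2 list.

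This can change who is analysed. Section 14.3 runs the primary analysis on the per-protocol set, which requires successful completion, and section 8.1 defines completion as attending all study visits. A subject stopped at Visit 4 already has primary endpoint data from Visit 3, but has none from Visit 6 and leaves the per-protocol set. A subject with the same finding at Visit 1 need not be lost under the listed criteria.

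**Working it through.** There is no figure in the plan to reproduce, so the check compares the two lists pattern by pattern.

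Rate each test (primary gaze, upgaze, push-up, in that order) as excessive (E), acceptable (A) or insufficient (I). That gives 3 × 3 × 3 = 27 patterns. The six-step criterion can be read in two ways: all three tests unacceptable in any direction, or all three unacceptable in the same direction.

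| Pattern | Six steps, any direction | Six steps, same direction | Step 4.14 |
|---|---|---|---|
| E/E/E | stop | stop | stop |
| I/I/I | stop | stop | stop |
| E/E/A | – | – | stop |
| E/E/I | stop | – | stop |
| E/I/E, E/I/I, I/E/E, I/E/I, I/I/E | stop | – | – |
| the other 18 | – | – | – |

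Totals listed as stops:
- Six steps, any direction: 1 + 1 + 1 + 5 = 8.
- Six steps, same direction: 2.
- Step 4.14: 4.

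Disagreements between the lists:
- Any direction: 1 pattern listed by 4.14 only (E/E/A) and 5 mixed patterns listed by the six steps only, 6 in all.
- Same direction: 2 patterns listed by 4.14 only (E/E/A and E/E/I), and none by the six steps only.

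Patterns that rate one lens excessive on one test and insufficient on another are unlikely in practice, so they carry no weight here. Patterns that do not mix E and I number 8 + 8 − 1 = 15 (those using only A and E, plus those using only A and I, less A/A/A, which is counted twice). Among these 15 the six steps list 2 (E/E/E, I/I/I) and 4.14 lists 3 (the same two and E/E/A). They differ on 3 − 2 = 1 pattern, E/E/A, under either reading, and 4.14 is the stricter.

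These are counts of patterns, not frequencies. They show where the rules part, not how many subjects are affected.

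**The case against.** The strongest reply is that the lists are not exhaustive. Step 1.27 says when a subject should not proceed; it does not say that every other fit is acceptable. Its closing sentence lets the investigator judge a lens unacceptable. Steps 1.31, 2.17, 4.18 and 5.17 require an acceptable general fit before dispensing, and section 8.2 gives unacceptable fit as a reason for withdrawal. An E/E/A lens could therefore be stopped at Visit 1 as well. This stands, and it narrows the gap. It does not close it: at Visit 1 stopping such a lens is left to judgement, while at Visit 4 it is a listed criterion.

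The second reply is that the Test-Control comparison is largely protected. The rule differs by period, not by lens; section 5.1 randomizes sequence, so each lens meets the stricter list in about half of the subjects; and the section 14.5 model includes period and sequence. This also stands, though model terms do not in themselves undo a loss of subjects after randomization.

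A reader might infer more than the documents support:
- **That the fit grades needed for the lens-fitting endpoint (section 2.2) are not recorded at Visit 4.** The visible text of 4.14 does not ask for separate grades. But Table 3 marks the same Lens Fit Assessment row at all six visits, the Appendix H procedure is redacted, and the eCRF is not shown. No gap in recording can be claimed.
- **That Visit 5 contradicts itself.** Step 5.9 ("Follow the fitting guide and steps 4.8-4.14 in Visit 4 Fitting") sends a refit through 4.14, and 5.10 then applies the other list. On E/E/A the stricter list comes first and nothing in 5.10 reverses it, so the outcome is not contradictory.
- **That the control lens package insert favours 4.14.** Among the possible signs of a flat fit it lists "excessive movement with the blink and/or edge standoff", and it advises against dispensing a lens judged flat. It covers the Control lens only, says nothing of up gaze, and on a literal reading one sign could be enough. It matches neither list.

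**Conclusion.** The inconsistency is real and can be read directly from the visible text; neither redaction nor any other section reconciles it. For a lens with excessive primary and upgaze movement and an acceptable push-up, the listed discontinuation rule differs between the two periods of the crossover.

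The severity is minor. The difference can affect who is discontinued, and so who enters the per-protocol set, but the number of subjects cannot be given because the documents do not state how often the pattern occurs. That the effect on the primary comparison is probably very small rests on randomized sequence, on period and sequence being modelled, and on the pattern being uncommon; the last is an assumption. A reader might go on to infer a bias for or against the Test lens. The documents do not support this, since each lens meets each list and nothing shows that either lens produces the pattern more often.

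**What to change.** Use one movement stop criterion at both fittings. By default, replace the two movement bullets of 4.14 with the criterion used in the other six steps, and add their instruction to grade centration, primary gaze, upgaze and push-up. Keep the overall acceptable/unacceptable rating that 4.14 already asks for. If the clinicians prefer the stricter two-test rule for excessive movement, put it in all seven steps (1.27, 2.10, 3.10, 4.14, 5.10, 6.10 and U.8) instead.

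The cost is a wording change and a check that the eCRF fields agree with it. No examination is added, and neither the sample size nor the analysis changes.
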